## I. BACKGROUND AND SIGNIFICANCE

Multiple lines of evidence suggest that gut microbiota play an important role in regulating human metabolism via effects on body weight and systemic insulin resistance. In rodents, manipulation of the gut flora with fecal microbiota transfer (FMT) induces weight loss and prevents development of obesity. In human studies, FMT administered via duodenal bowel lavage may confer benefits of short-term improvements in metabolic endpoints including insulin sensitivity. Recently, a new protocol for FMT has been developed at MGH utilizing oral capsulization that greatly improves the safety and feasibility of FMT as an investigative and therapeutic tool.

### Few safe and effective treatments for obesity

Over one-third of U.S. adults are obese and nearly a quarter have metabolic syndrome. Obesity and the metabolic syndrome are associated with disabling comorbidities and an increased risk for cardiovascular disease and mortality. Safe and effective treatments for obesity have been difficult to discover; indeed 4 FDA-approved drugs have been withdrawn from the market due to safety concerns. Bariatric surgery, while effective, is accompanied by high costs and potential morbidities and is therefore reserved for the most severe categories of obesity. Finding noninvasive low-cost alternatives to improve obesity and human metabolism is an imperative for our society.

### Effects of gut microbiota on energy balance

The gut microbiota is a diverse collection of several thousand species that actively participate in gut physiology and metabolic energy balance. These microbial species have been postulated to modulate energy absorption, gut motility, appetite, glucose and lipid metabolism, and hepatic fatty storage. The precise mechanisms by which gut microbiota perform these tasks are unclear. The dominant theories involve (1) increased energy harvesting from fermentation of foods otherwise indigestible to the host, (2) enlarging the nutrient absorption surface by promoting the intestinal epithelial growth, and (3) interaction with enteroendocrine cells to promote hormonal changes that influence host appetite and satiety, and (4) absorption of bacterial fragments such as lipopolysaccharides leading to “metabolic endotoxemia”, which promotes obesity and hyperinsulinemia.

### Gut microbiome and obesity

Intestinal bacteria have been implicated in the etiology of obesity. Animal studies have demonstrated that germ-free mice have lower body fat content than conventionally raised mice, an effect that is independent of diet. These germ-free mice are also resistant to diet-induced obesity. Genetically obese mice (ob/ob) have a reduction in the relative abundance of Bacteroidetes, with a proportional increase in Firmicutes. Importantly, similarly altered ratios of firmicutes:bacteroidetes and overall reductions in microbial diversity have been demonstrated in comparisons of obese and lean adults and in diabetic adults, although this finding has not been verified in all studies. Other studies have found that the obese state is accompanied by overall reductions in microbial diversity and a relative increase in pathogenic bacteria.

### Metabolic effects of altering the gut microbiome

Antibiotics are known to alter the community structure of the gut microbiome, and are associated with increased risk of becoming overweight in both animal and human studies. Interestingly, 7-day treatment with oral vancomycin led to a decrease in microbial diversity and was associated with a decrease in insulin sensitivity among men with metabolic syndrome.

A more directed method of altering the microbiome involves the direct delivery of donor fecal material into the gut. Colonization of germ-free mice with intestinal flora from obese mice led to greater increases in body weight and fat tissue than colonization with flora from lean mice. Other studies demonstrate that fecal microbiota transfer (FMT) from thin or obese adults can transmit the lean or fat phenotype when transplanted into mice, in the setting of the correct dietary conditions. Furthermore, fecal transplants from mice who sustained weight loss after gastric bypass surgery led to weight loss and improvements in insulin sensitivity among germ-free mice recipients. In human studies, fecal transfer from lean donors delivered at a single timepoint by duodenal bowel lavage led to improvements in insulin sensitivity at 6 weeks among men with metabolic syndrome, even in the absence of a dietary intervention.

### Skeletal effects of altering the gut microbiome

Recent data suggest that the gut microbiome may also have a direct impact on bone health. Germ-free mice have increased bone mass and decreased osteoclast number, and transplant of gut microbiota into germ-free mice led to normalization of bone mass. Antibiotics and probiotics causing shifts in the microbiota spectra can also increase bone mass in animals models (Ohlsson et al Endo Metab 2014). Mouse models have indicated that the gut microbiome has an effect on the immune system, hormonal pathways, and production of bacterial metabolites that could signal bone cells and affect bone density.

### Oral capsulized FMT protocol

Standard FMT protocols involve invasive procedures such as colonoscopy, nasogastric / duodenal tubes, or retention enemas, which are accompanied by procedural challenges, risks, and costs. Recently, we have developed a new FMT protocol that involves the capsulization of frozen fecal material. These oral capsules were highly effective in resolving otherwise refractory cases of *C. difficile* infection. The increased ease, tolerability, and safety of oral administration now allow study of FMT for sustained therapeutic intervention. This extended exposure is a major advance, and more likely to durably alter the microbiome.

### Contributions of this study to the field

We believe that transfer of the “lean” microbiota to an obese recipient may lead to weight loss and metabolic improvements. Therefore, we propose to conduct a randomized double-blind placebo-controlled pilot study to evaluate the safety and effectiveness of oral FMT administration on weight and metabolism in obese adults. This highly innovative study will leverage this new non-invasive FMT technique to promote durable changes in the gut microbiome, and could represent a new horizon of treatments for

obesity and insulin resistance. Future studies including microbiomic analysis may identify specific strains of beneficial organisms to help narrow treatments from generic FMT to specific probiotic strains. Identification of specific microbes and metagenomic pathways will also aid in our understanding of the mechanism by which the gut microbiome controls response metabolism.

## II. SPECIFIC AIMS

We propose a randomized placebo-controlled trial to study the impact of gut microbiome alterations on weight, insulin sensitivity, and other important metabolic endpoints.

**Aim 1.** To identify and characterize healthy lean donors from a phenotypic perspective to generate FMT capsules for a clinical trial in obese subjects.

**Aim 2.** To determine the impact of oral capsulized FMT from healthy lean donors on insulin sensitivity in obese adults in a 3-month randomized double-blind placebo-controlled trial. Secondary outcomes include changes in body weight, metabolic markers, and FMT-related adverse events. We hypothesize that FMT recipients will experience an improvement in insulin sensitivity and other metabolic endpoints. An optional extension study will evaluate the durability of gut microbiome change at 12 months.

**Aim 3.** To explore associations between the gut microbiome and bone density.

## III. PATIENT/SUBJECT SELECTION

Lean donors for FMT are being recruited from [name] IRB-approved protocol 2014P002706 "Placebo Controlled Study of Fecal Microbiota Transplant (FMT) for a second episode of *C. difficile* infection in adults using a frozen encapsulated inoculum". Lean donors must meet all the eligibility criteria as noted in protocol 2014P002706. Briefly, they must be age 20-60 years, have no significant past medical history, no use of antibiotics for the previous 6 months, and must pass a rigorous infectious disease screening protocol. In addition, donors must pass stricter weight and metabolic criteria than as outlined in protocol 2014P002706; in particular, they must have a BMI 18.5-23 kg/m^2 with no history of BMI exceeding 25 other than for pregnancy, stable weight for the preceding 6 months, and they must pass a 2-hour oral glucose tolerance test (fasting glucose <100 mg/dl, 2 hour OGTT glucose <140 mg/dl) to be eligible to donate for this obesity study.

24 obese recipients will be recruited to participate in the study from the greater Boston area. The obese recipients will be randomized 1:1 to weekly FMT vs. placebo capsules (n=12 FMT, n=12 placebo) for 6 weeks, with a total follow-up time of 24 weeks, or 12 months if they choose to participate in the optional substudy.

### Inclusion criteria

- BMI  $\geq 30$  kg/m^2 and stable weight for the previous 3 months
- Willingness to accept risk of unrelated donor stool.
- Age 25-60
- Able to consent for self in English language
- Subjects are not expected to receive antibiotics in the next 12 weeks.
- Patient must be willing to have screening labs for Hepatitis B and C, and HIV (as required by the FDA for past studies).
- Mild-moderate abnormal glucose metabolism: HOMA-IR  $>2.0$  or fasting plasma glucose  $\geq 100$  mg/dl; however subjects will be excluded for HOMA-IR  $>8.0$

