### Exclusion criteria

- Initiation or discontinuation of a medication known to affect body weight or insulin sensitivity within 3 months of enrollment (e.g. hormonal contraception, psychiatric medications: tricyclic antidepressants, monoamine oxidase inhibitors, paroxetine, escitalopram, lithium, olanzapine, clozapin, risperidone, carbamazepine, valproate, divalproex, mirtazapine)
- Use of weight-loss medications or diabetic medications in the preceding 1 year (e.g. metformin, sulfonyleureas, insulin, etc)
- Antibiotic use in the preceding 6 months
- Delayed gastric emptying syndrome
- Known chronic aspiration
- Swallowing dysfunction or oral-motor dyscoordination, or inability or unwillingness to swallow multiple large capsules
- Malabsorptive disorders including celiac disease, cystic fibrosis, irritable bowel syndrome, prior gastrectomy, bariatric surgery and any state of chronic diarrhea
- Pregnant women or women trying to conceive or women who are breastfeeding; women of child-bearing potential will have a urine or serum hCG test.
- Patients with an acute illness or an acute exacerbation of underlying co-morbid condition
- Subjects on high dose steroids ( $>40$  mg daily)
- Subjects on multiple/combination immunosuppressive regimens including high dose corticosteroids, calcineurin inhibitors, mTOR inhibitors, lymphocyte depleting biologic agents, anti-TNF agents.
- Patients with a history of HIV, hepatitis B, hepatitis C, decompensated cirrhosis, recent bone marrow transplant, other causes of severe immunodeficiency.
- Patients with a history of significant allergy to foods not excluded from the donor diet (excluded foods are tree nuts, peanuts, shellfish, eggs)
- Allergy to chocolate/cocoa or gelatin, or unwillingness to ingest gelatin (in placebo capsules).
- Screening labs: AST or ALT  $>3x$  normal; Hematocrit  $<33\%$ ; White Blood Cell count  $<3000$  cells/uL; ANC $<500$ ; Creatinine  $>2.0$  mg/dL
- Patients with abnormal bowel habits, e.g. constipation with  $<4$  bowel movements/week

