## **V. STUDY PROCEDURES**

Lean donors will undergo testing and follow procedures outlined in protocol 2014P002706. Main procedures will occur in the primary 12-week study period; a supplemental week 24 phone-call will be performed for a safety check. In addition, samples of the fecal collection will be stored at -80°C for further microbiome analysis.

Obese recipients will undergo the following procedures:

Phone Screen (10-20 minutes)

Screen Visit (30 minutes)

- Review eligibility and understand/see size of capsules
- Obtain informed consent
- Height, weight measurements to determine eligibility
- Screening labs: Complete blood cell count w/ differential, comprehensive metabolic panel, HIV Ab, HBV sAb/sAg, HCV Ab, fasting insulin and glucose.
- Subjects will be counseled not to start any new major dietary changes, exercise regimens, or medications throughout the primary 12-week study period
- Subjects will be given information about how to perform fecal collections (see Stool Collection document)

Baseline Visit, Week 0 (Day 1: 5 hours, Day 2: 15 minutes, Day 3: 15 minutes)

- Fasting blood samples for measurements of HOMA-IR, lipids, CRP, and HbA1c.
- Women of child bearing potential will have a urine pregnancy test
- Height, weight measurements
- 48-hour food recall
- Whole body DXA scan for body composition analysis
- DXA scan of lumbar spine and hip to assess baseline BMD (optional substudy)
- Fecal collection
- Indirect Calorimetry
- Hyperinsulinemic euglycemic clamp
- After above study procedures are complete, subjects will receive FMT (or placebo) caps, 15 capsules on each of 2 successive days. Note that participants will need to either fast for 4 hours after the clamp or return on the subsequent day for their first capsule administration.

Weeks 1-5 (15 minutes)

- Interval side effect assessment (see Side Effect Assessment document)
- Subjects return for weekly administration of 15 capsules (for a total of 6 weeks, including Week 0)
- Fecal collection at weeks 1, 3 and 5.

Week 6 (5 hours)

- Interval side effect assessment (see Side Effect Assessment document)
- Height, weight measurements
- Women of child bearing potential will have a urine pregnancy test

- Fasting blood samples for measurements of HOMA-IR, lipids, CRP, and HbA1c.
- 48-hour food recall
- Fecal collection
- Whole body DXA scan for body composition analysis
- Fecal collection
- Indirect Calorimetry
- Hyperinsulinemic euglycemic clamp

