- At 120 minutes, the insulin infusion will be discontinued, and the glucose infusion will continue for 30 more minutes. During this time, subjects will be given a meal. At 150 minutes, venous glucose will be checked, and the glucose infusion will be discontinued if venous glucose  $\geq 80$ mg/dL. If glucose is  $< 80$ mg/dL, the glucose infusion will be continued and will be weaned by the investigator at the bedside, with repeat venous glucose sampling every 10 minutes until the glucose is  $\geq 80$ mg/dL and the infusion is stopped.

- After the clamp, all subjects are counseled concerning the symptoms of hypoglycemia and are asked to report immediately any symptoms. Subjects are observed on the CRC for at least 20 minutes following discontinuation of glucose infusion.

This procedure assumes that the hyperinsulinemic state is sufficient to completely suppress hepatic glucose production and that there is no net change in blood glucose concentrations under steady-state conditions. Under such conditions, the rate of glucose infused is equal to the rate of whole-body glucose disposal (GDR) or metabolizable glucose (M) and reflects the amount of exogenous glucose necessary to fully compensate for the hyperinsulinemia.

Indirect Calorimetry: A ventilated hood calorimeter (VMAX Encore; Carefusion Corp, Yorba Linda, CA) will be utilized to assess resting energy expenditure (REE) and respiratory quotient (RQ) by determining oxygen consumption (VO2) and carbon dioxide production (VCO2) for 20 minutes under fasting conditions before the clamp. REE will be normalized to lean body mass as determined by dual-energy x-ray absorptiometry.

Compensation: Recipients will be compensated \$750 for completion of the study. \$100 for completing the baseline visit, \$400 for completing the week 6 visit (\$100 for the clamp visit, \$50 per capsule administration visit), and \$250 for the week 12 visit. If subjects choose to participate in the optional extension study, they will be compensated an additional \$100 (\$25 for 6 month visit and \$75 for 12 month, visit). They will also receive either a parking voucher or up to \$20 to cover travel expenses at each visit

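### The mild-moderate glucose criterion caps HOMA-IR but not fasting glucose, and the protocol does not say what happens when screening or week-0 labs show diabetes

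*Combined protocol and SAP*

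**What the plan says.** **Entry.** Section III, Inclusion criteria, has one item on glucose metabolism. It opens "Mild-moderate abnormal glucose metabolism: HOMA-IR", with a lower bound of 2.0, and offers fasting plasma glucose of at least 100 mg/dl as an alternative route. The upper bound follows: "mg/dl; however subjects will be excluded for HOMA-IR" above 8.0. No upper bound on glucose is given.

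**Exclusion.** The only exclusion that names diabetes treatment is "Use of weight-loss medications or diabetic medications in the preceding 1 year". A separate item excludes people who started or stopped a drug affecting weight or insulin sensitivity within 3 months of enrolment. Another excludes "Patients with an acute illness or an acute exacerbation of underlying co-morbid condition". The screening-lab limits cover liver enzymes, hematocrit, white cells, neutrophils and creatinine. Neither glucose nor HbA1c is among them.

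**Testing.** The screening labs in section V include "HIV Ab, HBV sAb/sAg, HCV Ab, fasting insulin and glucose". HbA1c first appears at the week 0 visit ("Fasting blood samples for measurements of HOMA-IR, lipids, CRP, and HbA1c"), with no eligibility role.

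**Counselling and referral.** At the screen visit, "Subjects will be counseled not to start any new major dietary changes, exercise regimens, or medications throughout the primary 12-week study period". The subject counselling paragraph in section V.C covers diet, exercise and hormonal treatment but has no general restriction on medications. Section VIII says subjects are referred to their own physicians when the study ends.

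**The concern.** The label tells the reader that recipients have mild to moderate disturbance of glucose metabolism. The limits that follow bound an insulin-resistance index, and that index can stay low while glucose is high if insulin is modest. A stable person with high fasting glucose who has taken no diabetes drug in the past year therefore meets the criterion as written.

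Two things are at stake. The first is safety. A screening result might call for treatment, yet one passage counsels against new medications for 12 weeks and no passage says what is done with such a result. The second is the primary outcome, change in insulin sensitivity over 12 weeks (section VI). Glucose-lowering treatment begun mid-trial would affect glucose and insulin, the two components of HOMA-IR. Section VI does not say how such data would be handled.

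**Working it through.** **1. The plan's own figure.** Section VI states 80% power with 12 per group after 15% dropout. Evaluable subjects: 12 × 0.85 = 10.2, taken as 10 per group. A two-sample t-test at two-sided 0.05 gives 80.5% for a 40% difference with SD 30%, and the same for 60% with SD 45%. The stated figure is reproduced. None of its inputs is an eligibility limit, so nothing below alters it.

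**2. Inputs for the eligibility check.** From section III: entry at HOMA-IR above 2.0 or fasting glucose of at least 100 mg/dl; exclusion at HOMA-IR above 8.0. Assumption: HOMA-IR = glucose (mg/dl) × insulin (uU/mL) / 405. The documents give no formula.

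**3. What the cap allows.** Setting HOMA-IR to 8.0 gives maximum insulin = 8 × 405 / glucose = 3240 / glucose.

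| Fasting glucose (mg/dl) | Highest insulin that passes (uU/mL) |
|---|---|
| 126 | 3240 / 126 = 25.7 |
| 160 | 3240 / 160 = 20.2 |
| 200 | 3240 / 200 = 16.2 |
| 250 | 3240 / 250 = 13.0 |

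The glucose values are illustrations, because the documents contain no diagnostic threshold for diabetes. In the other direction, maximum glucose = 3240 / insulin: 108 mg/dl at insulin 30, 162 at 20, 216 at 15 and 324 at 10.

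**4. The lower bound does not close the gap.** The two entry routes are alternatives. Anyone with glucose of 100 mg/dl or more qualifies by the glucose route, however low their insulin. At a glucose of 200, every insulin value up to 16.2 is admitted.

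**5. Dependence on the formula.** With any constant k in place of 405, maximum insulin is 8k / glucose, which is above zero at every glucose. The constant moves the figures in the table but cannot turn the cap into a glucose ceiling.

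**6. Whether another criterion fills the gap.** The drug rules remove anyone who begins a diabetes drug before enrolment. The acute-illness rule removes acute cases. Neither reaches a stable, untreated person. By contrast, section III gives lean donors explicit upper limits: fasting glucose below 100 mg/dl and 2-hour glucose below 140 mg/dl. Recipients have no counterpart.

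**7. What happens after enrolment.** The screen-visit text in section V includes medications in what subjects are counselled not to start. The counselling paragraph in section V.C does not. Section VIII places referral at the end of the study. The stop rules in sections V.E and V.F list no glucose result. Read together, these passages do not say what follows if screening or week-0 labs show diabetes.

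**The case against.** The strongest reply is that the label is only a heading defined by the limits beneath it, and that excluding diabetes drugs rather than the diagnosis may be deliberate. The cap also has some force at high glucose: at 200 mg/dl with insulin 20, HOMA-IR is 200 × 20 / 405 = 9.9, and the person is excluded. Passing at 200 to 250 mg/dl needs insulin no higher than about 13 to 16 in an untreated person with BMI of at least 30, and the documents do not say how common that is. All of this is fair. It limits how often the gap would matter but does not close it. If people with diabetes are meant to be eligible, the protocol should say so.

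A reader might infer more than the documents support:

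- **That needed treatment is forbidden.** The screen-visit text is counselling, and section V.C states it without a general medication restriction. The passages differ and need reconciling, but neither is a rule to withhold treatment.
- **That everyone found at screening to have diabetes would be enrolled.** Those who start a diabetes drug before enrolment are excluded.
- **That the clamp is unsuited to these subjects.** Section V.C states the assumption ("This procedure assumes that the hyperinsulinemic state is sufficient to completely suppress hepatic glucose production") but not that it fails above some fasting glucose. The dextrose rate may start at zero and is adjusted every 5 minutes, and the 110 mg/dL in the text is an example, not a limit. Section IV also calls the clamp a substudy by invitation, while section V lists it as a visit procedure.
- **That one or two such people would shift an arm mean.** The outcome is a change, so a high starting value alone does not bias it. The documents give no figure from which to calculate a shift.

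**Conclusion.** The point holds for eligibility and for the handling of results. As written, the criterion admits stable, untreated people with fasting glucose well above its lower bound: 126 mg/dl with insulin up to 25.7 uU/mL, through 250 mg/dl with insulin up to 13.0. That does not fit its label. The figures rest on the assumed HOMA-IR formula; the absence of a glucose ceiling does not. The number of people affected is unknown. The medication counselling and the referral text leave open what is done for them, and treatment begun mid-trial would affect the insulin-sensitivity outcome. This should be corrected, but it does not undermine the sample size: the stated power stands. No conclusion is drawn about the validity of the clamp or the size of any bias in the group comparison.

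**What to change.** In section III, make the criteria match the label. State whether people with diabetes are excluded, and add an upper fasting-glucose limit chosen by the sponsor, applied to the fasting glucose already drawn at screening. Keep the HOMA-IR limits.

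Reconcile the screen-visit counselling in section V, the subject counselling in section V.C and the referral statement in section VIII, so that the protocol says in one place what happens when screening or week-0 labs show diabetes. The content of that rule is for the sponsor and investigators to decide.

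The cost is a short amendment and a few more screen failures. No new test is needed, and the sample-size calculation is unchanged.
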